## Summary of versions and changes

Version	Description	Date approved
1	Initial version	2025-11-20

## 1 Background

One in ten adults in Region Stockholm have chronic kidney disease (CKD), which dramatically increases healthcare costs and the risk of poor patient outcomes, including cardiovascular disease and death. Identification and early management of these patients is done in primary care settings. However, most adults with CKD in our region are under detected, undiagnosed and undertreated, with low rates of referral to nephrology-specialist care.

In this pragmatic cluster-randomized controlled trial (RCT) among primary healthcare centers in Region Stockholm we seek to test the effect of a new electronic clinical decision support (CDS) triggering system to assist general practitioners through the guideline-recommended processes of CKD care of this large population segment.

## 2 Objectives

The objective of the ALMA study is to evaluate the effectiveness of the CDS trigger to ensure that people who meet the criteria for CKD testing are invited to test and are actually tested.

### 2.1 *Outcomes*

There are four key outcomes for this trial; one primary outcome (A) and three secondary outcomes (B, C, D). All four are binary outcomes.

	Comparison
A	Undergoing a creatinine test within 12 months of a visit at which time the patient was eligible for annual kidney function screening
B	Undergoing an albuminuria test within 12 months of a visit at which time the patient was eligible for annual kidney function screening
C	Undergoing a creatinine re-test within 6 months of the results of a creatinine test which indicated a re-test
D	Undergoing an albuminuria re-test within 6 months of the results of an albuminuria test which indicated a re-test

Eligibility for annual kidney function screening (outcomes A and B) is defined as a diagnosis of any one of the following:

- CKD
- hypertension
- diabetes
- cardiovascular disease
- nephrectomy

An indication for re-testing creatinine (outcome C) is having eGFR<60 ml/min/1.73 m^2 in the original test.

An indication for re-testing albuminuria (outcome D) is having a dipstick test denoting KDIGO A2+ or a urinary albumin to creatinine (uACR) test >3 mg/mmol in the original test.

## 2.2 Other secondary outcomes

There are four non-test related secondary outcomes:

**Outcome 2.1 CKD diagnosis:** Proportion of patients meeting indication who receive a diagnosis of CKD (according to ICD-10) within six months of eGFR / A2 re-testing. By “indication” we mean eGFR<60 ml/min/1.73 m^2 and/or dipstick A2+ or >3 mg/mmol at re-test. Only patients with at least six months of follow-up after their re-test and who are CKD-negative at the first visit will be included in this analysis (that is, re-test must occur on or before 30 June 2025).

**Outcome 2.2 Initiation of new CKD-treatment:** The proportion of patients who start new CKD-modifying treatment within six months of re-test indicating a CKD diagnosis (as defined above).

**Outcome 2.3 Referral for ultrasound:** The proportion of patients meeting the criteria for nephrologist care who receive a referral for ultrasound of the kidneys.

**Outcome 2.4 Accepted to nephrologist care:** The proportion of patients meeting the criteria for nephrologist care (according to Swedish guidelines) who are newly accepted into care. By “newly accepted” we mean we will exclude patients who have had a visit with a nephrologist in the two years prior to their first visit to a participating healthcare center during the trial period.

## 3 Study Methods

### 3.1 Trial design

This is a cluster-randomized controlled trial, with 66 healthcare centers randomized in a 1:1 ratio to either the new CDS trigger system (the intervention arm) or usual practice (the standard arm). The study includes all 66 Primary Healthcare centers in Region Stockholm, and is embedded in the Stockholm CREATinine Measurements project (SCREAM), which will enable us to have access to all relevant data for patients at these healthcare centers without need to modify clinical practice or perform active data collection.

There will be a four-month run-in period following randomization to allow clinicians to adjust to the new system. For data analysis purposes, recruitment into the trial will start on 1st January 2024.

### 3.2 Randomization

Randomization was restricted to ensure (approximate) balance on two factors, based on 2019 (pre-Covid) levels:

- Number of people eligible to be tested for albuminuria
- Proportion of people actually tested for albuminuria

We restricted the randomization as follows:

- There were four centers with an eligible population much larger than the other 62 centers

- Husläkarmottagning Handen = 5434
  - Ektorp = 4712
  - Liljeholmens vårdcentral = 3762
  - Jakobsberg vårdcentral = 3286
  - No other center had a 2019 eligible population greater than 3000
- We first created 10,000 randomizations of the 62 “non-large” centers, such that 31 were in each arm.
- We then created all possible permutations of the four large centers such that two were in one arm and two were in the other arm. There are six possible permutations which achieve this (AABB, ABAB, ABBA, BAAB, BABA, BBAA)
- We combined these two sets to give us 60,000 potential randomizations
- We then mirrored these allocations to give us 120,000 randomizations (that is, reversed the allocation of intervention and standard arms)
- For each potential allocation we calculated the average proportion of people tested in 2019. (This was calculated on a center level, not a population level, so the denominator was 33 in each arm.)
- If the difference in the average proportion between the arms was greater than 3.7% we discarded the allocation. The figure of 3.7% was chosen because, under different randomly drawn sets of the initial 10,000 allocations, 3.7% ensured that around, but less than, 10% of the final 120,000 allocations were discarded. And further, it was felt that 3.7% was small enough such that if there was indeed a between-arm difference of 3.7% we would still be confident that the two arms were similar enough to be confident of drawing unbiased conclusions from the results.
- Finally, one allocation was randomly selected from the remaining allocations

The code to perform this randomization was written by the trial statistician (SN) and then given to an independent statistician, outside of the study team, who changed the random seed which selected the 10,000 allocations, and the random seed which selected the final allocation. When the code was run, 10,348 (8.6%) allocations were removed due to a difference between the arms in 2019 test rates, and hence the final allocation was chosen from 109,652 possible allocations.

### **3.3 Post-randomization change**

Four days after randomization the study team were informed that two of the 66 centers had been merged into one administrative unit (although still on separate sites). These two centers were Bredäng and Sätra; their new name is “Bredäng Sätra vårdcentral”. Due to the merger we will not be able to retrieve outcome data at a lower level than the merged center. As by chance these two centers had been assigned to the same arm (the intervention) we decided to proceed with the trial under the original randomization. We note here that the two original restrictions still held after the merger of these centers:

1. the population of the new center is 1,455, which means it ranks 24th (of 65) in size
2. the difference between the two arms in terms of 2019 test rates is now 3.4% (< 3.7%)

This SAP is written to reflect that change. We will analyze the study with 65 centers (33 in the standard arm and 32 in the intervention).

### **3.4 Sample size**

The study was adequately powered to detect an absolute improvement in our primary study outcome of 13% with an alpha of 5%. To calculate the power of our trial, we evaluated the processes of care in the 66 primary healthcare centers during 2019 as collected in the SCREAM project. We chose this year prior to the COVID-19 pandemic to have more objective estimations of health use not affected by and policies during the pandemic. During 2019, 662 995 unique individuals visited those primary healthcare centers at least once. Of those, 92 011 were eligible for screening/testing of kidney function: 66% took a creatinine test, and 34% took a creatinine test. Of people with first detected eGFR<60 ml/min/1.73 m^2 or albuminuria, 59% and 28% were retested for creatinine or albuminuria within 3-6 months.

We assumed a recruitment period of 12 months and a total of 33 health center (clusters) per arm with the same number of patients as in 2019. We estimated the intraclass correlation for the outcomes to be 0.1 (as quantified in the UK trial by Major et al, J Am Soc Nephrol. 2019 Jul;30(7):1261-1270.). The table below gives the originally calculated power, and the power we now have, conservatively assuming 32 clusters per arm.

Comparison	Original power (33 clusters per arm)	New power (32 clusters per arm)
A. Primary outcome: Detect an increase of people having a creatinine test from 66% to 79%	86%	85%
B. Detect an increase of people having a albuminuria test from 34% to 48%	84%	83%
C. Detect an increase of people having a re-test of creatinine from 59% to 73%	86%	82%
D. Detect an increase of people having a re-test of albuminuria from 28% to 42%	86%	84%

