**Outcome D: Albuminuria re-testing**

Attribute	Description
Population	Adults who receive an abnormal albuminuria test result at a primary healthcare center of dipstick test denoting KDIGO A2+ or a urinary albumin to creatinine (uACR) test >3 mg/mmol and are thus indicated for a re-test within six months
Treatment	Intervention: New clinical decision support triggering system designed to manage chronic kidney disease, implemented at healthcare centers using the ALMA platform Control: Standard ALMA CDS platform
Endpoint	Undergoing an albuminuria re-test within six months of a test result which indicated a re-test
Summary measure	1. Ratio of proportions (risk ratio) 2. Absolute difference of proportions (risk difference)
Intercurrent events	As above

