#### 4.4 Analysis populations

The unit of observation is the individual patient. Each patient will only be included once in each analysis.

For outcomes A and B, each patient will be included at the time of their first visit during the recruitment phase: we will refer to this as their Index date for that outcome. This will be used as the start time for the 12 months window for testing.

For outcomes C and D, each patient will be included at the time of their results from their creatinine (C) or albuminuria (D) test: we will refer to this as their Index date for that outcome. This will be used as the start time for the 6 months window for re-testing.

There will be an analysis population associated with each of the four outcomes listed above (A-D). Randomisation occurred in September 2023; however, we will allow a four-month run-in period for the new system. Recruitment of individual participants will begin on 1st January 2024. For outcomes A and B, recruitment will close on 31st December 2024, to allow 12 months of follow-up for all patients. For outcomes C and D, recruitment will close on 30th June 2025, to allow six months of follow-up for all patients.

**Modified ITT population A:** All patients who attend a visit at one of the study health centers during 2024 and who remain alive and registered at that center for a further 12 months, and are eligible for annual kidney function screening.

**Modified ITT population B:** Same as Modified ITT population A (above)

**Modified ITT population C:** All patients who receive a test result for creatinine from one of the study health centers between 1st January 2024 and 30th June 2025, who remain alive and registered at that center for a further six months, and have an indication for a re-test.

**Modified ITT population D:** All patients who receive a test result for albuminuria from one of the study health centers between 1st January 2024 and 30th June 2025, who remain alive and registered at that center for a further six months, and have an indication for a re-test.

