### **6.2.1 Sub-group analysis 1: Repeat visits**

We will categorize each participant according to whether they attended one visit, or more than one visit, during the recruitment phase (12 months for outcomes A and B, 18 months for outcomes C and D). We will include this variable in the individual-level analysis model as an interaction with the treatment variable to assess if the intervention is more effective among patients who attend more frequently.

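### SAP Section 3.4: outcome C's two power figures (86% and 82%) cannot both follow from losing one cluster per arm, and the planning rates for C and D describe a narrower endpoint than the one analysed

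*SAP*

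**What the plan says.** Section 3.4 gives power for four outcomes, first as originally calculated with 33 clusters per arm, then as "the power we now have, conservatively assuming 32 clusters per arm". The stated pairs are:

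| Outcome | Rates | 33 per arm | 32 per arm |
|---|---|---|---|
| A (primary) | 66% to 79% | 86% | 85% |
| B | 34% to 48% | 84% | 83% |
| C | 59% to 73% | 86% | 82% |
| D | 28% to 42% | 86% | 84% |

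The row at issue reads "C. Detect an increase of people having a re-test of creatinine from 59% to 73" (per cent).

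The starting rates for C and D come from 2019 patients whose low eGFR or albuminuria was first detected in that year: "59% and 28% were retested for creatinine or albuminuria within 3-6 months". The same section says "We assumed a recruitment period of 12 months".

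Section 2.1 defines outcome C as "Undergoing a creatinine re-test within 6 months of the results of a creatinine test which indicated a re-test", and the estimand table for outcome D in Section 4.3.2 has "Undergoing an albuminuria re-test within six months of a test result which indicated a re-test". In Section 4.4 the six-month window opens at the index result, and populations C and D are patients with a result between 1 January 2024 and 30 June 2025 "who remain alive and registered at that center for a further six months, and have an indication for a re-test". Section 6.2.1 gives the recruitment periods as "12 months for outcomes A and B, 18 months for outcomes C and D".

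**The concern.** There are two faults in the same table.

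First, with rates, intraclass correlation (ICC), centre sizes and alpha held fixed, power depends on the number of clusters only through its square root. One cluster out of 33 is about 3% of the information. Rows A, B and D fall by 1 to 2 points, but row C falls by 4.

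Second, the 59% and 28% were measured on one definition of re-testing and the trial will report another. If early re-tests are common, the 2019 rates on the analysed definition are not 59% and 28%, and the targets of 73% and 42% are not on the scale of the reported outcome.

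At stake is what a reader is told the trial could detect on C and D after the merger, and whether the observed control-arm proportions can be compared with the planning assumptions.

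**Working it through.** **Inputs from the SAP.** Two-sided testing (Section 3.5). Alpha 5%, ICC 0.1, 33 then 32 clusters per arm, and 92 011 eligible patients in 66 centres in 2019, i.e. 92 011/66 = about 1,394 per centre for A and B (Section 3.4). The SAP gives no number per centre for C and D, no coefficient of variation (CV) of centre size and no power formula.

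**Step 1: row C without the unstated inputs.** Under the normal approximation, power = Φ(c√k − 1.96), where k is clusters per arm and c absorbs the effect size, ICC, centre size and CV.

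- *Forward from 86% at 33.* z(0.86) = 1.080, so at 32 clusters (1.960 + 1.080) × √(32/33) − 1.960 = 1.034, and power = 84.9%. Rounding of the 86% (85.5-86.5%) gives 84.4-85.5%. Stated: 82%.
- *Backward from 82% at 32.* z(0.82) = 0.915, so at 33 clusters (1.960 + 0.915) × √(33/32) − 1.960 = 0.960, and power = 83.1%. Rounding of the 82% (81.5-82.5%) gives 82.7-83.6%. Stated: 86%.
- *Clusters needed for the stated fall.* 33 × [(1.960 + 0.915)/(1.960 + 1.080)]² = 29.5 per arm (28.7-30.4 with rounding of both figures), not 32.
- *Largest possible fall.* Over all values of c, going from 33 to 32 costs at most 1.34 points. Unpooled, t-based, reduced-cluster and continuity-corrected variants reach at most 1.5 points. The stated fall is 4 points, and at least 3 after rounding.

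A t-based version (64 and 62 degrees of freedom) gives 86% to 84.9%, and 82% back to 83.2%.

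**Step 2: the other rows.** The same scaling takes 86% to 84.9% (A: stated 85%) and 84% to 82.9% (B: stated 83%). For D, an 86% that was really 85.5-86.5% becomes 84.4-85.5%, so a stated 84% fits by rounding. Only C fails.

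**Step 3: reproducing the table with a full formula.** Effective number per arm = k·m/DE, with DE = 1 + ((1 + CV²)m − 1) × 0.1, in a pooled-variance two-proportion z-test. With equal centres of 1,394, A is 96.3% and B 95.6% at 33 clusters, so the stated inputs alone do not give the table. A CV of 0.72, an assumption fitted here and not stated in the SAP, gives A 86.0/84.9 and B 84.4/83.3, matching both pairs. Solving the same formula for the centre size m behind the C and D figures:

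| Row | m for 86% at 33 | m for stated power at 32 |
|---|---|---|
| C | 118-301 | 44-56 (82%) |
| D | 166-1,042 | 95-178 (84%) |

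The ranges cover rounding. For D they overlap; for C they do not, so no single centre size yields both C figures.

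**Step 4: the endpoint behind the control rates.**

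| | 2019 planning rates (Section 3.4) | Analysis (Sections 2.1, 4.3.2, 4.4, 6.2.1) |
|---|---|---|
| Window | 3-6 months | up to 6 months, no lower limit |
| Patients | first-detected abnormality | all with an indicating result |
| Recruitment | 12 months | 18 months |

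For the same patients, the wider window can only raise the control rate. The effect of the wider population on the rate has no sign that can be read from the SAP. As illustration only (assumed 100 patients per centre, CV 0.72, 32 clusters, the 14-point gain kept):

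- C: 80.8% at a control rate of 50%, 84.1% at 59%, 91.6% at 70%.
- D: 83.6% at a control rate of 28%, 80.1% at 40%.

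**The case against.** Section 3.4 does not name its power method. If the figures were simulated, Monte Carlo noise could widen the gap: with 1,000 replicates per cell, a difference between two cells near 85% has a standard error of √(2 × 0.85 × 0.15/1,000) = 1.6 points, and the excess over the expected fall (4 − 1.1 = 2.9 points) is about 1.8 of these. Nothing in the SAP points to simulation, however, and rows A and B follow a formula. Even if noise were the cause, the printed pair would still misstate the cost of the merger.

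The centre-size back-calculation carries a CV fitted to A and B over to different populations. That is a fair limit; Step 1 does not need it.

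On the control rates, the 3-6 month wording may be loose for by six months, and if so a sentence settles the window. Each patient enters each analysis once, which brings the analysed population nearer to first detection, but it does not exclude patients with known disease. Longer recruitment is not harmful: it adds patients and makes the 12-month assumption conservative on numbers. It remains a difference between the planned and analysed populations.

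Finally, both C figures exceed 80%, C and D are secondary, and the SAP was approved on 2025-11-20, after recruitment for them closed on 30 June 2025. No recalculation can alter the design or the estimates. That stands and limits the importance of the point, but not its correctness.

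**Conclusion.** Both parts hold. At least one of outcome C's two power figures is wrong. The stated loss is 4 points against about 1.1 points from one cluster per arm, and this rests only on the cluster count being the sole change, as Section 3.4 states. The document does not show whether 86% or 82% is the error.

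The C and D control rates, as worded, belong to a narrower endpoint and population than those analysed. The size of that effect cannot be derived from the SAP, and the illustrative powers depend on assumed centre sizes, CV and control rates.

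The consequence is limited to the stated sensitivity for two secondary outcomes. It should be corrected, but it does not threaten the primary outcome row or any planned analysis.

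**What to change.** 1. Recheck the outcome C calculation and correct whichever figure is wrong.
2. For C and D, recompute the 2019 control rates, numbers per centre and power using the Section 2.1 window and the Section 4.4 populations. Alternatively, state in Section 3.4 that the 59% and 28% refer to first-detected abnormalities re-tested at 3-6 months, with 12 months of recruitment. If the 3-6 month phrase was meant as by six months, say so.
3. When the table is restated, give the formula and the CV of centre size actually used.

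The cost is a recalculation from 2019 data already held, a few table cells and a sentence. It needs no more patients and no change to the analysis.

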### **3.5 Framework**

This will be a superiority study, with two-sided p-values and confidence intervals for all comparisons.

### **3.6 Statistical interim analysis and stopping guidance**

There is no planned interim analysis, and no pre-specified stopping guidance.

### **3.7 Timing of final analysis**

The final analysis will be performed 24 months after the start of the recruitment phase (that is, after the initial run-in period). Hence the cutoff point for measuring outcomes is 31st December 2025.

## 4 STATISTICAL PRINCIPLES

### 4.1 Confidence intervals and p-values

We will calculate 95% confidence intervals throughout. No formal statistical significance level will be set.

### 4.2 Adherence and Protocol deviations

The trial intervention is implemented at the level of the cluster (health center). As such, we do not anticipate any protocol deviations or lack of adherence. If other clusters are merged during the duration of the study we will handle this on a pragmatic, case-by-case basis. If the two centers are in the same arm we will continue without change. If the two centers are in different arms, the decision as to which diagnostic system to use will be made by us in collaboration with Region Stockholm.

### 4.3 Definition of estimands

Following the estimands framework defined in the European Medicines Agency “ICH E9 (R1) addendum”, we here define estimands for the main trial objectives. For each outcome we will report risk ratios as the primary population-level summary (effect size), and risk difference as a secondary measure.

#### 4.3.1 Primary estimand

Attribute	Description
Population	Adults who visit a primary healthcare center and are indicated for annual kidney function screening
Treatment	Intervention: New clinical decision support triggering system designed to manage chronic kidney disease, implemented at healthcare centers using the ALMA platform Control: Standard ALMA CDS platform
Endpoint	Undergoing a creatinine test within 12 months of first visit in 2024
Summary measures	1. Ratio of proportions (risk ratio) 2. Absolute difference of proportions (risk difference)
Intercurrent events	1. Death (from any cause): Exclude from analysis 2. Patient transfers to (has visit with) another healthcare center in this trial: use outcome value, and analyze according to the randomisation group of the original healthcare center

#### 4.3.2 Secondary estimands

##### Outcome B: Albuminuria testing

Attribute	Description
Population	Adults who visit a primary healthcare center and are indicated for annual kidney function screening
Treatment	Intervention: New clinical decision support triggering system designed to manage chronic kidney disease, implemented at healthcare centers using the ALMA platform Control: Standard ALMA CDS platform
Endpoint	Undergoing an albuminuria test within 12 months of first visit in 2024

Summary measure	1. Ratio of proportions (risk ratio) 2. Absolute difference of proportions (risk difference)
Intercurrent events	As above

